12 PARTICIPANT SAFETY MONITORING AND REPORTING

12.1 Institutional Review Boards

The study protocol, consent form, and other study documents will be submitted to Duke University IRB for approval. Any amendments to the protocol, other than minor administrative changes, must be approved by each Duke University IRB before they are implemented.

12.2 Adverse Event Definition

An adverse event (AE) is any untoward medical occurrence associated with the use of a drug in a participant, whether or not considered drug or biologic related. An AE can therefore be any undesirable sign, symptom or medical condition occurring after starting study drug, even if the event is not considered to be related to the pharmaceutical product.

12.3 Suspected Adverse Reaction Definition

A suspected adverse reaction (SAR) is any adverse event for which there is a reasonable possibility that the drug caused the event. “Reasonable possibility” suggests there is a causal relationship between the drug and the adverse event. “Suspected adverse reaction” implies a lesser degree of certainty about causality than adverse reaction, which means any adverse event caused by a drug.

12.4 Serious Adverse Events (SAE)

An adverse event or suspected adverse reaction is considered serious if the investigator or sponsor believes any of the following outcomes occurred:

- Death
- Life-threatening AE: Places the subject at immediate risk of death at the time of the event as it occurred. It does not include an AE that, had it occurred in a more severe form, might have caused death.
- Persistent or significant incapacity or substantial disruption of the ability to conduct normal life functions.
- Inpatient hospitalization or prolongation of hospitalization.
- Congenital anomaly or birth defect.
- Important medical events that may not result in death, be life threatening, or require hospitalization may be considered a serious adverse event when, based upon appropriate medical judgment, they may jeopardize the participant and may require medical or surgical intervention to prevent one of the outcomes listed in this definition above. This determination is based on the opinion of the investigator.

12.5 Laboratory Test Abnormalities

For laboratory test abnormalities that meet the definition of an SAE, that required the participant to have the investigational product discontinued or interrupted or require the participant to receive specific corrective therapy, the clinical diagnosis rather than the laboratory term will be used by the reporting investigator (e.g., anemia versus low hemoglobin value).

12.6 Assessment of Causal Relationship

A medically-qualified investigator must assess the relationship of any AE to the use of study drug, based on available information, using the following guidelines:

- **Not related:** There is not a reasonable causal relationship to the investigational product and the adverse event.
- **Unlikely related:** No temporal association or the cause of the event has been identified, or the drug or biologic cannot be implicated.
- **Possibly related:** There is reasonable evidence to suggest a causal relationship between the drug and adverse event.
- **Related:** There is evidence to suggest a causal relationship, and the influence of other factors is unlikely.

12.7 Assessment of Adverse Event Severity

The determination of adverse event severity rests on medical judgment of a medically-qualified investigator. The severity of AEs will be graded using the following definitions:

- **Mild:** Awareness of sign, symptom, or event, but easily tolerated;
- **Moderate:** Discomfort enough to cause interference with usual activity and may warrant intervention;
- **Severe:** Incapacitating with inability to do usual activities or significantly affects clinical status, and warrants intervention.

12.8 Recording and Reporting of Adverse Events

The site Investigator is responsible for monitoring the safety of subjects enrolled into the study.

All AEs occurring from signed informed consent through study visit 3 will be captured on the AE eCRF. For patients who die during the course of the study, the cause of death will be reported by the investigator in the eCRF. The Duke Heart Center Clinical Research Unit will share all SAEs with Novartis Pharmaceuticals within 24 hours after the investigators are made aware. AE reports will be shared with Novartis Pharmaceuticals, as requested.

Any misuse or abuse of the study drug, other medication errors and uses outside of what is foreseen in the protocol (irrespective of whether a clinical event has occurred) will also be documented in the eCRF.

12.9 Follow-up of Adverse Events

When additional relevant information becomes available, the investigator will record follow-up information according to the same process used for reporting the initial event as described above. The Investigator will follow all reportable events until resolution, stabilization or the event is otherwise explained.

Investigators are also responsible for promptly reporting AEs to Duke University IRB in accordance with local requirements. The Data Safety Monitoring Board (DSMB) will review detailed safety data approximately every 6 months throughout the study.

12.10 Expectedness

The expectedness of an AE or Suspected Adverse Reaction (SAR) shall be determined according to the most current patient package insert (PPI). Any AE that is not identified in nature, severity, or specificity in the current PPI is considered unexpected. Events that are mentioned in the PPI as occurring with a class of drugs or as anticipated from the pharmacological properties of the drug, but not specifically mentioned as occurring with the particular drug under investigation are considered unexpected.

12.11 Suspected Unexpected Serious Adverse Reaction

AEs that meet the criteria of serious, related to study drug, and unexpected per PPI, qualify for expedited reporting to the regulatory authorities. The site Investigator will assess all SAE's occurring at his/her site and evaluate for "unexpectedness" and relationship to study drug. The site Investigator is required to complete and submit a voluntary MedWatch Report for events viewed as serious, study drug related and unexpected at:

<https://www.accessdata.fda.gov/scripts/medwatch/>.

12.12 Pregnancy

Pregnancy occurring during a clinical investigation, although not considered a serious adverse event, will be recorded in the eCRF. Study drug will be discontinued among patients confirmed to be become pregnant during the study. The pregnancy will be followed until final outcome. Any associated AEs or SAEs that occur to the mother or fetus will be recorded in the AE/SAE eCRF,. The pregnancy outcome of a female partner to a male study participant will not be followed.

13 STATISTICAL METHODS AND DATA ANALYSIS

13.1 General Design Issues

Planned analyses will be prospectively defined for this study prior to unblinding of data.

Primary analysis of the PARACOR-19 trial will be based on the intention to treat (ITT) principle. That is, subjects will be analyzed (and endpoints attributed) according to the treatment strategy to which subjects are randomized, regardless of subsequent additional post-randomization treatment and medical care. The ITT population will correspond to all randomized subjects. Secondary analysis will include per-protocol analysis, which will include randomized patients who remain on assigned study drug and complete the entirety of the study protocol.

Statistical comparisons will be performed using two-sided significance tests. Baseline demographic and clinical variables will be summarized for each randomized arm of the study. Descriptive summaries of the distribution of continuous variables will be presented in terms of percentiles (e.g., median, 25th and 75th percentiles) along with means and standard deviations.

Categorical variables will be summarized in terms of frequencies and percentages.

In addition, exploratory analyses will be performed to help explain and understand findings observed from the planned analyses. Statistical tests with a 2-sided p-value <0.05 will be considered statistically significant, unless otherwise stated. Analyses will be performed using SAS software (SAS Institute, Inc, Cary, NC).

13.2 Sample Size Justification and Randomization

Subjects will be randomized in a 1:1 allocation ratio. We plan to randomize approximately 50 participants with planned follow-up of 12 weeks. Given the exploratory nature of this early phase study, the co-primary endpoints (relative change in hs-troponin T, relative change in sST2) will be assessed separately using a type 1 error of 0.05.

We assume a 25% relative reduction in hs-troponin T compared with placebo at 12 weeks, and a 25% relative reduction in sST2 compared with placebo at 12 weeks. A two-sided, two-sample t-test with group sample sizes of 25 and 25 achieves at least 80% power to detect a ratio of 0.75 when the ratio under the null hypothesis is 1.00. The coefficient of variation (CV) on the original scale is assumed to be ≤ 0.36 which is reasonable based on historical data.¹⁸ The significance level (alpha) is 0.05. As the CV decreases, the statistical power increases; however, if the CV increases we would need to find a larger ratio to have at least 80% power. For example, if the CV were actually 0.57, then we would have 80.3% power to find a significant ratio of 35%. For all primary and exploratory biomarker endpoints, values below the lower limit of the assay will be imputed with values just below the level of detection, consistent with approaches in prior cardiovascular biomarker trials.¹⁸

13.3 Interim Analyses and Safety Reviews

It is anticipated that the DSMB will review the accumulating data and schedule ad hoc meetings if SAEs accrue. During such meetings, the DSMB may be provided the following information: subject enrollment reports, rates of adherence with the assigned treatment, and description of SAEs. The DSMB will review data masked by study group (such as X vs. Y). Due to the size of the trial, no formal interim analysis of efficacy is planned. There will be no futility analysis.

13.4 Analysis of the Co-Primary Endpoints

For each serum biomarker, we will calculate the ratio of geometric means at baseline and 12 weeks for the sacubitril/valsartan treatment arm compared with the placebo arm, with 95% confidence intervals. A two-sample t-test will be used to test for a significant difference using a p-value <0.05 for each co-primary endpoint. A sensitivity analysis will be done using generalized linear regression to assess the ratio after adjusting for possible baseline differences.

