7.2 Inclusion Criteria

1. Patient with a history of laboratory proven-diagnosis of COVID-19 who is 4-16 weeks

from their last positive COVID-19 test

2. Systolic blood pressure ≥ 100 mmHg at screening
3. ≥ 18 years of age
4. Successful collection of baseline serum biomarkers
5. Successful completion of baseline EQ-5D questionnaire
6. Successful completion of baseline CMR study (CMR sub-study only)
7. High-sensitivity troponin at or above the level of detection on screening labs
8. Presence of ≥ 1 of the following:
 - a. Age ≥ 60
 - b. History of atherosclerotic cardiovascular disease (ASCVD), including myocardial infarction, coronary artery disease, ischemic stroke/transient ischemic attack, or peripheral artery disease
 - c. Diabetes mellitus (Type 1 or Type 2)
 - d. Body mass index ≥ 35 kg/m²
 - e. eGFR 30-60 ml/min/1.73m²
 - f. History of atrial fibrillation/flutter

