11 OUTCOME DETERMINATIONS

11.1 Primary Endpoints

1. Relative change from baseline in high-sensitivity troponin T levels from randomization to 12 weeks.
2. Relative change from baseline in sST2 from randomization to 12 weeks.

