13.5 Analysis of Exploratory Endpoints

Serum biomarker exploratory endpoints will be assessed in an identical manner to the co-primary endpoints.

CMR exploratory endpoints will be analyzed as change from baseline using linear regression (with treatment, randomization group assignment, and the baseline value as covariates) to determine estimated mean, the differences compared with placebo, and 95% confidence intervals (CI). Sensitivity analyses will be considered adjusting for possible baseline differences.

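### A free gain in precision, not an error: the co-primary t-test ignores the measured baseline; a prespecified log-baseline ANCOVA would add about 1 to 9 points of power at assumed correlations of 0.9 to 0.5

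*Combined protocol and SAP*

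**What the plan says.** Section 11.1 defines the first co-primary endpoint as "Relative change from baseline in high-sensitivity troponin T levels from randomization to 12 weeks"; the second is the same measure for sST2. Section 13.2 sizes the trial for a two-sample comparison of 25 against 25, and each endpoint "will be assessed separately using a type 1 error of 0.05".

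Section 13.4 reports ratios of geometric means and sets the test: "A two-sample t-test will be used to test for a significant difference using a p-value <0.05 for each co-primary endpoint". No covariate is mentioned. Baseline enters only through a secondary step: "A sensitivity analysis will be done using generalized linear regression to assess the ratio after adjusting for possible baseline differences". Which baseline variables are meant is not stated.

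Three other places bear on this:
- Section 7.2, item 4 makes "Successful collection of baseline serum biomarkers" a condition of entry, so the covariate is available by design.
- Section 13.5 analyses the exploratory CMR endpoints by linear regression "with treatment, randomization group assignment, and the baseline value as covariates".
- Section 13.5 also says: "Serum biomarker exploratory endpoints will be assessed in an identical manner to the co-primary endpoints". Whatever is chosen in 13.4 therefore extends to the exploratory serum biomarkers.

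**The concern.** On the log scale, relative change is log(12-week value) minus log(baseline value). A t-test on that difference is a regression on baseline with the slope fixed at 1. If the variances at the two visits are equal, the true slope equals the correlation between them, which is below 1. The change score then over-corrects: the arm that happens to start higher tends to show the larger fall.

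The t-test's standard error already allows for this, so type I error is not at risk. The cost is a wider interval than the data require. Stated power is only just above 80% in about 50 patients, with no dropout allowance, and section 8.7 rules out permuted blocks and stratification, so the design does nothing to limit chance imbalance in baseline values.

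There is also a matter of prespecification. Section 13.1 says "Planned analyses will be prospectively defined for this study prior to unblinding of data", yet the adjusted ratio in 13.4 has no named covariate and is still open to choice.

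**Working it through.** **Inputs from the plan (section 13.2).** Ratio 0.75, CV 0.36, 25 per arm, two-sided alpha 0.05.

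**Inputs not in the plan (assumed).** Correlation ρ between log baseline and log 12-week value, taken as 0.5, 0.7 and 0.9. Equal log variances at the two visits. The t-test is applied to log change, and CV 0.36 describes the variability of the relative change; the other reading of the CV is in step 5.

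**1. Reproduce the plan.**
- Log SD: σ = √ln(1 + 0.36²) = 0.349.
- Effect: δ = ln 0.75 = −0.288.
- Standard error: 0.349 × √(2/25) = 0.0987. Non-centrality: 0.288/0.0987 = 2.91.
- Non-central t on 48 df gives **81.5%** power, in line with the stated minimum of 80%.
- The plan's second scenario (CV 0.57, 35% reduction, so ratio 0.65) gives 80.3%, exactly as stated.

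**2. Power with log baseline as covariate.**
- Single-visit SD: σ/√(2(1−ρ)).
- Residual SD after adjustment: single-visit SD × √(1−ρ²) = σ√((1+ρ)/2).
- Residual df: 47. Estimating the slope multiplies the variance of the treatment effect by about 1 + 1/46 on average.

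| | ρ = 0.5 | ρ = 0.7 | ρ = 0.9 |
|---|---|---|---|
| Residual SD | 0.302 | 0.322 | 0.340 |
| Power before slope cost | 90.9% | 87.2% | 83.3% |
| Power with slope cost | 90.3% | 86.5% | 82.5% |
| Gain over 81.5% (points) | about 9 | about 5 | about 1 |
| 95% CI half-width, log scale (t-test 0.199) | 0.174 | 0.185 | 0.196 |
| Per-arm n for the t-test to match | 33 | 29 | 26 |
| Extra patients in total, 2 × (n − 25) | 16 | 8 | 2 |

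At ρ = 0.95 power is 81.6%, so there is almost no gain.

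**3. Simulation check.** With 200,000 trials per correlation, the t-test gives 81.4% to 81.5% and the adjusted model 90.4%, 86.5% and 82.6%. In a separate run of 40,000 trials per cell, both tests rejected a true null in 4.9% to 5.2% of trials.

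**4. What a chance imbalance does to the change score.** The SD of the between-arm difference in mean log baseline is the single-visit SD (0.349, 0.451, 0.781) × √(2/25) = 0.099, 0.127, 0.221. Multiplying by (1−ρ) gives shifts of 0.049, 0.038 and 0.022 log units. A one-SD imbalance therefore moves the estimated ratio by about 5%, 4% or 2%.

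**5. Other reading of the CV.** If 0.36 describes the level at one visit, the SD of log change is 0.349 × √(2(1−ρ)). The planned test then has 81.5%, 95.8% and about 100% power, against 90.3%, 97.7% and about 100% for the adjusted model. The gain is about 9, 2 and 0 points.

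**6. Unequal variances.** Hold the SD of log change at 0.349 and include the slope cost. If the 12-week SD is 1.15 times the baseline SD, adjusted power is 86.6%, 82.7% and 80.8%. At 1.3 times it is 84.1%, 81.0% and 83.8%. At 0.8 times with ρ = 0.7 it is 94.6%. The largest loss among these cells is 81.5 − 80.8 = 0.7 points.

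**The case against.** The case for leaving the plan alone has five parts.

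- **The plan already adjusts.** Section 13.4 includes a baseline-adjusted regression, and the t-test is valid and matches the sample-size calculation. In a small exploratory trial, which of two sound analyses comes first is close to preference. It stands that nothing is wrong with the test. But a sensitivity analysis with unnamed covariates sets neither the primary p-value nor the primary interval.
- **The gain rests on a correlation the documents do not give.** This stands. If CV 0.36 describes the log change, ρ = 0.5 implies a single-visit 95% range of only about 4-fold between patients, and ρ = 0.9 implies about 21-fold. The entry criteria admit a mixed population, so the smaller gains are at least as plausible as the 9-point one.
- **Equal variances may fail.** This also stands. The 1-to-9 range is not a bound, and some cells show a slight loss. The downside found was under one point.
- **Troponin has a floor.** Screening troponin must be detectable at entry, while low 12-week values are imputed just below the limit. That could disturb a log-linear slope. A simulation that floors both visits at the level holding an assumed 15% of baseline values does not support the worry: power was 85.5% against 68.6% at ρ = 0.5 and 75.6% against 71.6% at ρ = 0.9, with type I error near 5%. It does not model selection at entry exactly.
- **The change is not cost-free in process.** Sections 12.1 and 16.2 require IRB approval of amendments that are more than administrative. This is correct, and the cost is stated under the fix.

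**Conclusion.** The point holds as a recommended improvement, not as an error. The planned test is valid, its type I error holds and its stated power reproduces. It sets aside a covariate that every participant must have, and so gives the co-primary endpoints a less precise analysis than the exploratory CMR endpoints receive.

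The gain is about 9, 5 or 1 points of power at correlations of 0.5, 0.7 or 0.9, and next to nothing at 0.95. This assumes equal log variances at both visits and a CV of 0.36 for the relative change. Where the true gain falls cannot be settled from the documents. The recommendation does not depend on that, because the possible loss is very small and the possible gain is worth up to 16 patients.

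**What to change.** In section 13.4, make the primary analysis of each co-primary endpoint a linear model for log(12-week value), with randomised treatment and log(baseline value of the same biomarker) as the only prespecified covariate. Using log change as the outcome with the same covariate gives the same treatment estimate. Report the exponentiated treatment coefficient as the geometric mean ratio, with its 95% CI and p-value. Keep the unadjusted t-test on log change as the sensitivity analysis.

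Section 13.5 then carries the model to the exploratory serum biomarkers without further change. The sample size in 13.2 can stay as it is.

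The cost is a wording amendment, with IRB approval, before unblinding, and one residual degree of freedom (48 to 47). It needs no new data and no additional patients.

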13.5 Analysis of Exploratory Endpoints

Serum biomarker exploratory endpoints will be assessed in an identical manner to the co-primary endpoints.

CMR exploratory endpoints will be analyzed as change from baseline using linear regression (with treatment, randomization group assignment, and the baseline value as covariates) to determine estimated mean, the differences compared with placebo, and 95% confidence intervals (CI). Sensitivity analyses will be considered adjusting for possible baseline differences.

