7 PATIENT POPULATION

7.1 Study Population

It is anticipated that approximately 50 participants meeting eligibility criteria listed below will be randomized into the study. It is anticipated that 30 of these patients will be included within the CMR substudy. Individuals suitable for this protocol are patients with cardiovascular risk factors and 4-16 weeks from prior COVID-19 infection.

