8.7 Randomization, Stratification and Blinding

Patients will be consented and enrolled at the first study visit. Eligible patients will be randomized in a 1:1 allocation ratio to one of two treatment groups. Since this is a single center pilot study, randomization will not involve a permuted block design or any stratification.

Blinding of the study, with respect to treatment groups, will be preserved by the use of matching placebo. The investigator may be asked at the end of the trial if they had obtained any

information which may have led to the unblinding of treatment.

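### Does listing both treatment and randomization group assignment in the CMR regression leave the treatment effect undefined?

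*Combined protocol and SAP*

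**What the plan says.** Section 13.5 (Analysis of Exploratory Endpoints) specifies a linear regression of change from baseline for the CMR endpoints, "with treatment, randomization group assignment, and the baseline value as covariates". Its stated purpose is "to determine estimated mean, the differences compared with placebo, and 95% confidence intervals (CI").

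Four other places bear on what the first two covariates can mean:

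- Section 8.7: "Eligible patients will be randomized in a 1:1 allocation ratio to one of two treatment groups", and "randomization will not involve a permuted block design or any stratification".
- Section 13.1, primary analysis: subjects are analysed "according to the treatment strategy to which subjects are randomized".
- Section 13.1, per-protocol analysis: this set holds "randomized patients who remain on assigned study drug and complete the entirety of the study protocol".
- Section 7.1, size of the sub-study: "It is anticipated that 30 of these patients will be included within the CMR substudy".

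No section defines treatment and randomization group assignment as different things. The plan gives no power or precision figure for the CMR regression.

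**The concern.** The sentence in section 13.5 reads as a list of three covariates, and nothing marks the second as an explanation of the first. In a stratified trial the second might be a stratum or block, but this trial has neither. Under intention to treat, treatment is the randomised arm. In the per-protocol set, where everyone stays on assigned drug, it is the arm again. A regression with two identical columns has no unique value for the coefficient labelled treatment.

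An analyst who wanted to keep the two terms distinct might take treatment to mean drug actually taken. Section 10.2 keeps patients who stop study drug in follow-up through visit 3, so drug taken and arm could differ. The treatment coefficient would then be identified only by patients who departed from their assignment. It would not be the randomised comparison, it would be open to adherence bias, and it would be less precise.

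This one sentence is also the only analysis specified for LVEF, LVEDVi, LVESVi, native T1, native T2 and the two focal-fibrosis measures. If it failed, the whole CMR sub-study would lack a defined analysis.

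**Working it through.** **Inputs.** Two arms, 1:1, no strata or blocks (section 8.7); analysis as randomised (section 13.1); 30 CMR patients (section 7.1). A 15/15 split is assumed for illustration. Allocation without blocks does not guarantee it, but the algebra below needs only that both arms contain patients.

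**1. The model as written.** Let T be treatment, G randomization group and B the baseline value:

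change = α + β₁T + β₂G + γB + error.

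With T = G for every patient this becomes

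change = α + (β₁ + β₂)T + γB + error.

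The design matrix [1, T, G, B] has 4 columns and rank 3.

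**2. What can be estimated.** A numerical estimability check on 30 simulated patients gave:

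| Quantity | Estimable? |
|---|---|
| β₁ alone | no |
| β₂ alone | no |
| β₁ + β₂ | yes |

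An active and a placebo patient with the same baseline value b have expected changes α + β₁ + β₂ + γb and α + γb. Both are estimable, and their difference is β₁ + β₂. Only the split between the two coefficients is arbitrary.

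**3. Comparison with the single-term model.** In the same simulated data set:

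| Model | Arm difference |
|---|---|
| Both terms (minimum-norm solution) | 1.01 + 1.01 = 2.02 |
| Arm and baseline only | 2.02 (SE 1.39; 95% CI −0.83 to 4.87) |

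Both matrices have rank 3 and span the same space, so the fitted values and the residual degrees of freedom (30 − 3 = 27) agree too. The standard error and confidence interval for the difference are therefore also the same.

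**4. Where software could stumble.** If both terms are entered as classification factors, the default adjusted mean for one treatment level averages equally over the two levels of the other factor. For the active arm that is α + t₁ + ½g₀ + ½g₁. No patient has t₁ with g₀, so this is not estimable. A program would report a non-estimable quantity rather than a wrong number. Removing either term gives the result in step 3.

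**5. The drug-taken reading.** Suppose k of 15 active-arm patients are off drug (assumed; the documents give no rate). Setting the baseline covariate aside and holding residual variance fixed, drug taken has a sum of squares of k(15 − k)/15 once arm is in the model. Arm alone has 15 × 15/30 = 7.5. The ratio of standard errors is √{7.5 ÷ [k(15 − k)/15]}:

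| k | k(15 − k)/15 | SE ratio |
|---|---|---|
| 1 | 0.933 | 2.83 |
| 2 | 1.733 | 2.08 |
| 3 | 2.400 | 1.77 |
| 5 | 3.333 | 1.50 |

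That loss would be real under this reading. But the two standard errors belong to different quantities, and section 13.1 attributes endpoints by randomised strategy whatever treatment follows. The reading is not available under the plan.

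**The case for a change.** The best case for a change is that it costs a few words and would remove reliance on an unstated repair. Section 13.1 promises that analyses will be defined before unblinding, yet the model as listed has a redundant term, and default adjusted means may come back as non-estimable. The analyst must then depart from the written list. The drug-taken reading is also awkward in that it would run without any warning.

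Part of this stands. The two terms are aliased, their separate coefficients are not estimable, and no section says that the second merely explains the first.

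The rest does not carry. The non-estimable flag is visible, and collapsing the alias gives the same number whichever column is dropped, so the repair leaves no room for a choice made after seeing the data. The drug-taken reading conflicts with section 13.1, and in the per-protocol set it reduces to the arm.

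A further reading is possible. Sections 6.1 and 10.1 set the starting-dose tier by systolic pressure at randomisation in both arms, and randomization group could loosely mean that tier. The documents never call it that. If it were meant, the tier would be a covariate fixed before treatment and not determined by arm. The model would ordinarily have full rank with 30 − 4 = 26 residual degrees of freedom, and the treatment coefficient would still be the randomised comparison. Striking the term would then remove a covariate that was intended.

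**Conclusion.** No change follows. Section 13.5 names the arm twice, which is a clerical redundancy. The quantities it asks for are unique under the duplicated model and identical to those from a regression on randomised arm and baseline value. The effect on any estimate, confidence interval or conclusion is zero; the only practical cost is a possible software flag for default adjusted means, which the analyst resolves by keeping one arm term.

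This rests on treatment meaning randomised arm, which section 13.1 supports for the primary analysis and, through its definition, for the per-protocol set. It does not depend on the assumed 15/15 split. The reach is small in any case: exploratory CMR endpoints in about 30 patients, with no power claim attached. The co-primary t-tests in section 13.4 and the sample size in section 13.2 do not use this model.
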